Test Session: The schedule of events during the test sessions is shown in Table 2. The sessions will begin around 8 AM, following overnight nicotine abstinence. Before the session begins, participants will have two indwelling catheters placed in antecubital veins, one for administering infusions and one for collecting blood samples. A blood sample will be drawn prior to the first infusion to measure baseline levels of plasma nicotine and menthol glucuronide and for women, additional samples for the measurement of estradiol and progesterone levels will be collected. Baseline measurements will then be collected including heart rate, blood pressure, self-report assessments and cognitive testing. Participants will then receive the assigned infusion over a period of ten minutes. Psychometric assessments and blood sampling will then continue for the next 120 minutes. Participants will be discharged after evaluation by the study physician. Participants will also receive their assigned cigarettes at the end of the session.

Table 2. Schedule of Events: Test Session*

Time point (min)	Measures and Events
Baseline	CO, urine and blood samples, HR/BP, M-NWSC, BQSU, SAFTEE, CPT
0	IV Infusion 1 (nicotine over 2.5 min or 5min) starts
1	HR, DEQ, plasma nicotine
3	HR, DEQ, plasma nicotine
5	HR, DEQ
6	plasma nicotine
8	HR, DEQ
10	IV Infusion 1 ends, HR, DEQ, BQSU,
12	plasma nicotine
13	HR, DEQ,
15	HR, DEQ, plasma nicotine
18	HR, DEQ
20	HR, DEQ, plasma nicotine
25	HR, DEQ,
30	HR/BP, DEQ, BQSU, CPT, M-NWSC, MCP
45	HR, DEQ, BQSU, M-NWSC CPT, plasma nicotine
60	IV Infusion 2 (Saline) starts
61	HR, DEQ, plasma nicotine
63	HR, DEQ, plasma nicotine

65	HR, DEQ
66	plasma nicotine
68	HR, DEQ
70	IV Infusion 2 ends, HR, DEQ, BQSU,
72	plasma nicotine
73	HR, DEQ,
75	HR, DEQ, plasma nicotine
78	HR, DEQ
80	HR, DEQ, plasma nicotine
85	HR, DEQ,
90	HR/BP, DEQ, BQSU, CPT, M-NWSC
105	HR, DEQ, BQSU, M-NWSC CPT, plasma nicotine
120	IV Infusion 3 (nicotine over 2.5 min or 5min) starts
121	HR, DEQ, plasma nicotine
123	HR, DEQ, plasma nicotine
125	HR, DEQ
126	plasma nicotine
128	HR, DEQ
130	IV Infusion 3 ends, HR, DEQ, BQSU,
132	plasma nicotine
133	HR, DEQ,
135	HR, DEQ, plasma nicotine
138	HR, DEQ
140	HR, DEQ, plasma nicotine
145	HR, DEQ,
150	HR/BP, DEQ, BQSU, CPT, M-NWSC
165	HR, DEQ, BQSU, M-NWSC CPT, plasma nicotine
180	End of session, HR/BP, DEQ, plasma nicotine, M-NWSC, BQSU, SAFTEE, MCP
190	Discharge

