*Saline infusions will follow each nicotine infusion to maintain a 10-min total infusion time for each test session. Abbreviations: CO: Alveolar carbon monoxide; HR/BP: Heart rate/Blood pressure; M-NWSC: Minnesota Nicotine Withdrawal Symptom Checklist; BQSU: Brief Questionnaire of Smoking Urges; CPT: Continuous Performance Test; DEQ: Drug Effects Questionnaire; SAFTEE: Systematic Assessment for Treatment Emergent Events. MCP: Money choice procedure.

7) Statistical analysis and sample size estimates

Specific Aim #1: To examine if switching from menthol to non-menthol cigarettes will change the dose-effect curves for positive subjective effects and alleviation of smoking urges as a function of nicotine delivery rate.

Positive subjective effects of nicotine will be assessed with the “Like the Drug Effects” and “Good Drug Effects” items from the DEQ, consistent with the FDA Guidance on abuse potential assessment (10). These items have been shown to correlate with the abuse potential of drugs of abuse. Effects will be tested using linear mixed effects models with peak change on each DEQ item as a response variable, cigarette-assignment (menthol vs. non-menthol), phase (1 vs.2) and nicotine delivery condition as within-subject factors and their interaction. Random effects for subject and condition within subject will be used to account for correlations between

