repeated measures. Because of the potential skewed distributions of the subjective effects data, transformations will be applied as necessary. We will evaluate the main and interactive effects of cigarette assignment and delivery rate. We anticipate statistically significant main effects of cigarette assignment, nicotine delivery rate and a significant interaction between cigarette assignment and nicotine delivery rate. To better understand the dose effects of nicotine delivery rate and whether they are moderated by cigarette assignment, we will construct specific contrasts among the four doses to test whether there is an indication of significant linear, quadratic, linear on log-scale or sigmoidal dose-response relationships across, or within menthol-preference groups. The possible dose-response curves identified by the specific mean contrasts will be compared by fitting linear and non-linear (as necessary) dose-response models with continuous dose and selecting the best-fitting model by the Akaike's Information Criterion (AIC). To test for an effect of delivery rate on smoking urges, assessed by the BQSU (Factor 1 and 2) scores, we will use similar modeling approach described for subjective effects, but we will also include time as a within-subject factor with outcomes for minute 0, 10, 30, 60 and 120. We anticipate a significant main effect of menthol-preference, nicotine delivery rate and potentially a significant interaction between cigarette assignment and nicotine delivery rate.

Exploratory Aim#1: To explore the dose-effect curves of nicotine delivery rate for a) reinforcement (assessed with the Multiple-Choice Questionnaire), b) heart rate and blood pressure, and c) tobacco withdrawal severity, assessed with self-report symptoms and cognitive performance.

The primary outcome for the analysis of reinforcement will be the crossover point determined by the monetary choice procedure for the four infusion conditions. The crossover point is the monetary value at which a subject chooses money over receiving the infusion for that condition. It is a continuous measure (dollar amount) from -20 to +20 with values > \$0 indicating reinforcement. Tobacco withdrawal severity is measured by the MNWS and CPT taken at 0, 30, 60 and 120 min after the beginning of infusion. The models will be similar to the one described for Specific Aim #1 with time as an additional within-subject factor for heart rate, blood pressure and tobacco withdrawal severity.

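### Exploratory blood pressure is to be modelled over time, but saline has one scheduled reading, so nicotine-versus-saline comparisons are confined to +30 min

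*Combined protocol and SAP*

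**What the plan says.** In section 7) Statistical analysis and sample size estimates, Exploratory Aim#1 covers heart rate and blood pressure as outcome group (b). Its models follow Specific Aim #1, "with time as an additional within-subject factor for heart rate, blood pressure and tobacco withdrawal severity". The same paragraph gives times for another outcome, "Tobacco withdrawal severity is measured by the MNWS and CPT taken at 0, 30, 60 and 120 min after the beginning of infusion", but none for blood pressure.

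Table 2 (section 9, C, Test Session) distinguishes HR from HR/BP. HR/BP appears in five rows:

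- Baseline: "CO, urine and blood samples, HR/BP, M-NWSC, BQSU, SAFTEE, CPT"
- 90 and 150 min: "HR/BP, DEQ, BQSU, CPT, M-NWSC" (the 30-min row lists the same measures plus MCP)
- 180 min: "End of session, HR/BP, DEQ, plasma nicotine, M-NWSC, BQSU, SAFTEE, MCP"

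The last measures before infusions 2 and 3, at 45 and 105 min, are "HR, DEQ, BQSU, M-NWSC CPT, plasma nicotine": heart rate without blood pressure. The 60-min row reads "IV Infusion 2 (Saline) starts" and lists no measure. The 120-min row likewise only starts infusion 3.

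Section 9, B) Drugs fixes saline as the second infusion. Medical monitoring (section 9, C) makes nicotine conditional on systolic pressure below 150 mmHg and has a monitor attached. It sets no reading times and does not designate those readings as outcome data.

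**The concern.** In a model with a placebo infusion, a time factor is useful because it lets the course after nicotine be compared with the course after saline. If saline is read once, it has no course to compare. If an infusion has no reading just before it, change from its own starting value cannot be calculated.

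At stake is how far the placebo-controlled blood pressure result reaches. It would describe one moment, 25 to 27.5 min after nicotine stops, while the analysis text promises a description over time. An analyst following the text would fit a time factor informed only by the nicotine infusions.

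**Working it through.** The plan gives no figure on this point, so the check is a count of Table 2 followed by an estimability argument.

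**Step 1. Convert clock times to minutes from each infusion's own start (0, 60, 120).**

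| Infusion | pre | +30 | +60 |
|---|---|---|---|
| 1, nicotine | baseline | 30 | none |
| 2, saline | none | 90 | none |
| 3, nicotine | none | 150 | 180 |

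Filled cells per session: 2 + 1 + 2 = 5 of 9. The only time shared by all three infusions is +30.

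**Step 2. Pool the two nicotine orders.** If each rate comes first in some sessions and last in others, each rate has pre, +30 and +60. Filled cells: 3 + 3 + 1 = 7 of 9. For both rates, pre comes only from infusion 1 and +60 only from infusion 3.

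**Step 3. Degrees of freedom.** An additive condition-plus-time model has 1 + 2 + 2 = 5 parameters. The full condition-by-time interaction has (3 − 1)(3 − 1) = 4 df.

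- One session: 5 − 5 = 0 of 4.
- Orders pooled: 7 − 5 = 2 of 4. These equal (2 − 1)(3 − 1) = 2, the 2.5- versus 5-min comparison over three times. None involves saline.
- Full grid: 9 − 5 = 4 of 4.

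The additive model can be fitted in every case.

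**Step 4. Smallest addition that fills the grid.** The nine cells need clock positions 0, 30, 60, 90, 120, 150 and 180. Only 60 and 120 are missing, so two readings suffice: 5 become 7 per session. Taken at about min 59 and 119, each is the approximately +60 value of one infusion and the pre value of the next.

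**Step 5. Do shared readings still carry 4 df?** The six changes are 30 − B, 59 − B, 90 − 59, 119 − 59, 150 − 119 and 180 − 119, where B is baseline and each number stands for the reading at that minute. They link seven readings without a closed loop, so they are linearly independent (rank 6), and the four between-condition contrasts at +30 and +60 have rank 4. In change-score form these are 2 df for condition plus 2 df for condition by time: the same 4 df.

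**Step 6. Drift.** For the raw +30 contrast of saline with the mean of the two nicotine infusions, 90 − (30 + 150)/2 = 0, so linear session drift cancels. For changes to +30, with every pre reading 1 min before its infusion, 31 − (31 + 31)/2 = 0. Table 2 does not time the baseline reading. If it were taken 15 or 30 min before infusion 1 (assumed values), the imbalance would be 31 − (45 + 31)/2 = −7 min or 31 − (60 + 31)/2 = −14.5 min.

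**Step 7. Carry-over into the saline reference.** Min 59 falls 59 − 5 = 54 to 59 − 2.5 = 56.5 min after nicotine stops in infusion 1. Suppose a residual pressor effect r remains at min 59 and has gone by min 90. Saline's change, 90 − 59, is lowered by r, and nicotine minus saline is raised by r. The documents give no value for r.

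**Step 8. Heart rate for comparison.** It is scheduled for all three infusions at +1, 3, 5, 8, 10, 13, 15, 18, 20, 25, 30 and 45: 12 shared times, against 1 for blood pressure.

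**The case against.** **The plan does not name the term.** It adds time as a factor and stresses the interaction of cigarette assignment with delivery rate. Condition by time for blood pressure is inferred from the description of the models as similar. This stands. The confinement of saline to +30 and the missing pre-infusion values do not depend on it.

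**The aim concerns delivery rate, and rates can be compared over time.** This also stands. A reader might infer that blood pressure has no estimable time course, or that the aim cannot be answered. Step 3 shows otherwise: both pooled interaction df belong to the rate comparison.

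**A mixed model tolerates incomplete data.** It does when some participants supply the missing cells. Here the saline cells are empty by design for everyone. Reading time as session clock does not help: saline coincides with minute 90, so the two are aliased.

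**The safety check supplies readings.** It implies a pressure check near min 120, so one added reading may already be taken. It implies none before saline, because the rule governs nicotine. A reader might infer a safety conflict from Table 2's silence; the Medical monitoring rule applies regardless, so there is none.

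**The added readings miss the peak.** The Biomarkers text expects delivery rate to alter peak plasma nicotine and not AUC, so a rate effect is most plausible early. This stands as a limit. Every heart-rate time from +1 to +25 is also a DEQ time, and Specific Aim #1 uses "linear mixed effects models with peak change on each DEQ item as a response variable", which is a reason for caution about cuff readings there. The +6 and +12 rows have plasma sampling only, so an early reading is not ruled out. The proposal completes the saline comparison; it does not capture the peak.

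**Shared readings complicate the change scores.** They do: min 59 and 119 enter neighbouring infusions' changes with opposite signs, and residual nicotine can bias the saline change. Both need handling in the analysis.

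**Conclusion.** The point holds for the saline comparison only. As scheduled, nicotine versus saline on blood pressure can be assessed at +30 min and nowhere else, infusions 2 and 3 lack a scheduled reference value, and no condition-by-time term involving saline is estimable (saline fills 1 of its 3 cells). The 2.5- versus 5-min comparison over pre, +30 and +60 is estimable with orders pooled, subject to the tie between time and infusion position in step 2.

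This assumes that Table 2 is the complete schedule of outcome readings, that time runs from each infusion's start, that each session contains both rates, and that both nicotine orders occur.

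Two further inferences are unsupported. The +30 contrast is not shown to be biased by session drift, since linear drift cancels. Heart rate does not share the defect; it too lacks a reading immediately before infusions 2 and 3, but its shared times support a time factor for saline. Primary outcomes, randomisation and sample size are unaffected. This is an optional, inexpensive improvement to an exploratory analysis.

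**What to change.** 1. Add blood pressure to Table 2 just before infusions 2 and 3, at about min 59 and 119. If the pre-infusion-3 safety check is already done, record it as data.
2. Take the baseline pressure last in the baseline block, so that all three reference values sit just before an infusion.
3. In Exploratory Aim#1, name pre, +30 and +60 as the blood pressure times, and analyse change from each infusion's own pre value at +30 and +60.
4. Use a within-session covariance that allows for the shared 59 and 119 min readings.
5. Report the raw +30 contrast as a sensitivity analysis, because it does not use the min 59 reference.

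Cost: two cuff cycles per session on equipment already attached, or four per participant over two sessions (10 readings become 14), plus a Table 2 edit and brief analysis text. Neither new time coincides with a blood draw, DEQ rating or running infusion; the last scheduled measures are 14 min earlier (59 − 45 and 119 − 105). The remaining downside is the possible inflation of nicotine minus saline described in step 7.

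If no readings can be added, state that saline contrasts for blood pressure are limited to +30 min, and keep the pooled nicotine-rate comparison over time. That needs only a text edit.

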Smokers will be recruited from the New Haven area through newspaper, and radio advertisements and fliers. The study will be described over the telephone. Subjects will be given a brief tobacco use history and medical screening questionnaire. Eligible subjects will be invited to a screening evaluation. The screening evaluation will include the following: a) obtaining an informed consent; b) tobacco use history, the Fagerstrom Test of Nicotine Dependence (FTND) and DSM-5 Tobacco Use Disorder (TUD) criteria; c) urine cotinine levels determined with a NicAlert test strip; d) complete physical and psychiatric examination including the structured clinical interview (SCID) for DSM-5 criteria; e) laboratory examination including CBC, TSH, ALT, AST, GGT, alkaline phosphatase, glucose, BUN and creatinine; f) urine analysis for drug screening, and for women, urine pregnancy test.

To minimize the risk of COVID-19 transmission, every attempt will be made to conduct the screening procedures that do not require in-person interaction, like physical and laboratory examination, remotely by video or phone. Consent form and other self-report forms will be mailed to the participants before the sessions and they will be asked to return these documents when they come to the medical center for screening.

Inclusion criteria: 1) Female and male smokers, aged 21 to 59 years, who have been smoking tobacco cigarettes for at least a year; 2) smoke ≥ 5 and less than 30 cigarettes per day; 3) urine cotinine levels > 100 ng/mL consistent with nicotine intake of an active smoker (23); 4) not seeking treatment at the time of the study for nicotine dependence; 5) in good health as verified by medical history, screening examination, and screening laboratory tests; and 6) for women, not pregnant as determined by pregnancy screening, nor breast feeding, and using acceptable birth control methods.

Exclusion criteria: 1) history of major medical or psychiatric disorders that the physician investigator deems as contraindicated for the subject to be in the study; 2) regular use of psychotropic medication (antidepressants, antipsychotics, or anxiolytics); 3) current alcohol or substance dependence for any other recreational or prescription drugs other than nicotine; 5) urine drug screening indicating recent illicit drugs use (with the exception of marijuana).

8: Recruitment:

Approximately, 50 subjects will be recruited, to have 38 completers.

9. Research Plan:

A) Measures

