Nicotine administration: Nicotine bitartrate will be obtained from Interchem Corporation, Paramus, NJ, and solutions for IV injection will be prepared by U.S. Specialty Formulations, Bethlehem, PA. On the morning of each test session, weight-adjusted nicotine and saline solutions will be prepared by the West Haven VA research pharmacy. Nicotine and saline will be administered using an infusion pump connected to an IV catheter located in a forearm vein. We have followed these procedures in our previous studies, which were completed without any serious adverse effects attributed to nicotine or other safety concerns. [name] holds an ITP (Investigational Tobacco Product) for IV nicotine administration. A new ITP application has been submitted to the FDA for this project.

In each test session, there will be a total of 3 infusions. Each infusion duration will be 10 minutes long, which will be achieved by infusing saline for the remainder of the time following the 2.5- and 5-minute nicotine infusions. A research nurse, will program 2 infusion pumps to administer nicotine or saline solutions. For the 2.5 and 5 min infusion conditions, participants will first receive nicotine for 2.5 and 5 minutes, followed by saline infusions. For the saline condition, participants will receive saline for 10 minutes. The participants will be blind to the randomization. The order of infusions will be: 1) 5-min or 2.5-min nicotine infusion, 2) saline infusion and 5-min or 2.5-min infusion. This infusion order was chosen to minimize carry over effects between nicotine infusions. Participants will be blind to the order of nicotine infusions.

Justification for the nicotine doses and infusion rates: The total nicotine dose for each test session will be 2 mg/70 kg body weight, a dose within the range of nicotine delivered by smoking 1 or 2 tobacco cigarettes or e-cigarettes (21). For safety reasons, the maximum dose of nicotine for each infusion will be 1 mg. The infusion rates will be 0.096 and 0.048 $\mu\text{g}/\text{kg}/\text{second}$ over 2.5 and 5 minutes, respectively.

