Exploratory Aim#2: To examine the impact of plasma nicotine levels and rate of nicotine metabolism (measured by plasma hydroxy cotinine/cotinine ratio) on the dose-effect curves for the main study outcomes.

To address this aim, we will use a similar mixed model approach to the one described for specific aim #1. For plasma nicotine levels, we will include peak plasma and area under the curve (AUC) nicotine plasma concentration as a continuous predictor instead of nicotine delivery condition in separate mixed models. The AUC will be calculated using the nine nicotine concentrations collected across the 120-minute sampling period.

For the rate of nicotine metabolism, the plasma hydroxy cotinine/cotinine ratio will be included as a continuous predictor in the model.

Exploratory Aim#3: To examine sex differences for the main study outcomes.

To evaluate whether sex moderates' menthol and nicotine delivery rate effects we will add sex as an additional factor in all models above.

Rationale for sample size: With 30 individuals, the study will have over 80% power to detect large effect sizes ($f=0.4$) for the comparisons of the menthol and non-menthol conditions ($f=0.6$ or higher) on alleviation of the subjective effects and similarly large effect sizes for the interaction between condition and nicotine delivery rate ($f=0.65$ or higher) at Bonferroni-adjusted level of 0.025. To account for 20% dropout, we will recruit approximately 38 subjects.

11. Risks and benefits:

Potential risks

There are potential risks, discomforts and inconveniences associated with the participation in this study. These may be due to nicotine administration, blood drawing, and other study procedures.

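### The number 38 is the recruited total in the sample-size rationale but the completer total in section 8, and the power sentence gives f=0.4 and f=0.6 for one comparison without defining f

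*Combined protocol and SAP*

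**What the plan says.** Two places in the combined protocol and SAP set the size of the trial.

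- **Rationale for sample size** (end of the statistical analysis section): "With 30 individuals, the study will have over 80% power to detect large effect sizes", followed by "To account for 20% dropout, we will recruit approximately 38 subjects". Here 30 is the evaluable number and 38 the recruited number.
- **Section 8, Recruitment**: "Approximately, 50 subjects will be recruited, to have 38 completers". Here 38 is the evaluable number and 50 the recruited number.

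The power sentence in the rationale prints three effect sizes. It first refers to "large effect sizes ($f=0.4$) for the comparisons of the menthol and non-menthol conditions". For that same comparison it then adds a second value in parentheses: "for the comparisons of the menthol and non-menthol conditions ($f=0.6$ or higher". The third value is "for the interaction between condition and nicotine delivery rate ($f=0.65$ or higher) at Bonferroni-adjusted level of 0.025".

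The rationale does not define f, name the test behind the calculation, or give a within-subject correlation. It also does not say how many levels nicotine delivery rate has. The section on nicotine administration says "In each test session, there will be a total of 3 infusions": two nicotine rates and one saline infusion. The statistical analysis section refers to four doses and four infusion conditions.

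**The concern.** Both sections use the verb recruit, so they describe the same step, and 38 cannot be both the number entering and the number finishing. The plan therefore does not settle when enrolment stops, how many people will be exposed to intravenous nicotine, or which n the power statement describes.

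The effect sizes raise a separate question. An over-80% claim is informative only if the reader knows the smallest effect it covers. With two values for one comparison and no definition, a reader could take f=0.4 as an effect the trial can detect. Whether that is true depends on a definition the plan does not give.

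**Working it through.** **Enrolment.** Inputs are 30, 38 and 20% from the rationale, and 50 and 38 from section 8.

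- Rationale: 30 / (1 − 0.20) = 37.5, rounded up to 38. The plan's figure reproduces.
- Section 8: 1 − 38/50 = 0.24, an implied loss of 24%.
- Section 8 at the rationale's own rate: 38 / 0.80 = 47.5, rounded up to 48, which is close to the approximate 50.

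Each pair is coherent alone. The conflict is in the targets: 38 or 50 recruited, 30 or 38 evaluable.

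**Power, first scale (assumed).** Noncentrality λ = n·f², level 0.025. This is a paired comparison with f read as the standardised mean within-subject difference. The menthol versus non-menthol test is F(1, n−1).

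| n | f | λ | Power |
|---|---|---|---|
| 30 | 0.6 | 30 × 0.36 = 10.8 | 81.6% |
| 30 | 0.4 | 30 × 0.16 = 4.8 | 44.2% |
| 38 | 0.6 | 38 × 0.36 = 13.68 | 90.8% |
| 38 | 0.4 | 38 × 0.16 = 6.08 | 55.6% |

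The smallest f with 80% power is 0.59 at n=30 and 0.52 at n=38. So f=0.6 fits the printed over 80% at n=30, and f=0.4 does not.

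**Interaction on the same scale.** With k delivery levels the test is F(k−1, (k−1)(n−1)).

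| Delivery levels | Power at f=0.65, n=30 | 80% limit, n=30 | 80% limit, n=38 |
|---|---|---|---|
| 2 | 87.7% | 0.59 | 0.52 |
| 3 | 81.5% | 0.64 | 0.56 |
| 4 | 76.4% | 0.67 | 0.60 |

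The printed 0.65 falls just above 80% only with three levels.

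**Power, second scale (assumed).** f is a raw repeated-measures f over two conditions, with λ = 2·n·f²/(1−ρ), F(1, 29), n=30 and level 0.025. The documents give no ρ, so a range is shown for f=0.4.

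| ρ | Power at f=0.4 |
|---|---|
| 0 | 76.5% |
| 0.1 | 81.1% |
| 0.3 | 90.3% |
| 0.5 | 97.4% |

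Power at f=0.4 reaches 80% at ρ of about 0.08. At that correlation f=0.6 has 99.1%, so 0.6 is then far from the detection limit.

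On neither scale are 0.4 and 0.6 both the smallest effect detectable with 80% power.

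**The case against.** The strongest reply is that nothing here shows a miscalculation. Each recruited/completer pair is coherent. The 0.4 stands in parentheses directly after the words for a large effect, so it may be only a conventional label, with 0.6 and 0.65 as the effects actually powered. Much of this stands. The 44% rests on an assumed definition of f, and on another definition 0.4 does exceed 80%. But the sentence does not say that 0.4 is a label, and the two roles of 38 remain whatever f means.

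A second defence is that 50 are screened and 38 randomised. Section 8 says completers, and no other text supports a screening reading.

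Three stronger readings are tempting, and the documents do not support them.

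- A reader might infer that the sections assume different dropout rates, 20% against 24%. Section 8 states no rate. The 24% comes from dividing two approximate numbers, and 20% loss on 38 completers gives 48, which approximately 50 can cover.
- A reader might apply the 24% to 38 recruits (38 × 0.76 = 28.9) and infer that power could slip under 80%. That mixes one section's recruitment with the other's implied loss, and neither section plans it.
- A reader might infer that the trial is underpowered. For the menthol comparison at f=0.6, both sections' own completer numbers give over 80% on either scale above (correlation zero or positive on the second). For the interaction, the answer depends on a number of levels that the plan does not fix.

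**Conclusion.** Wrong as written, and worth correcting. The recruitment targets differ by 12 people (50 against 38) and the evaluable targets by 8 (38 against 30), with no reconciling text. This half needs no assumption.

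The second half is a real clash in the power sentence, but its size is conditional. On n·f² with 30 completers, power is 82% at f=0.6 against 44% at f=0.4. On a raw repeated-measures f with correlation above about 0.08, f=0.4 is adequately powered, and f=0.6 understates what the trial can detect. The definition of f, the F tests and the correlations are assumptions, because the plan states none of them. The supported conclusion is that the design size and the detectable effect are not determined by the text, not that the trial is too small.

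**What to change.** 1. Put one recruited/completer pair and one dropout rate in both section 8 and the sample-size rationale. The choice is the sponsor's:
   - 38 recruited and 30 completers at 20% dropout; or
   - about 50 recruited and 38 completers (48 at 20%, or 50 at 24%), with power restated for 38. On n·f² that is 91% for the menthol comparison at f=0.6, with an 80% limit of 0.52.
2. Delete the f=0.4, or label it as a benchmark that is not an effect the trial is powered for.
3. Beside the detectable effects, state the definition of f, the test, any assumed correlation and the number of delivery levels. If the definition is n·f², take the interaction limit from the table above for the chosen n and number of levels.

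The edits are to text, but item 1 needs a sponsor decision on the enrolment and completer targets. Neither option exceeds the enrolment already planned in section 8.
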